Randomized trial of holding vs. continuing incretin-based therapies before upper endoscopy

Principal Investigator:

[name].

Email: [contact]

Address: [name]

Background:

Incretin-based therapies include GLP-1 receptor agonists (GLP-1RAs) and dual GLP1-RA and gastric inhibitory polypeptide (GIP) agonists. These drugs are commonly prescribed for diabetes and more recently, their use has risen exponentially as a primary therapy for weight loss. These medications can decelerate gastric emptying and diminish bowel motility by inhibiting peristalsis at the GLP-1 receptors situated in myenteric neurons. Therefore, there exists a theoretic potential for gastroparesis, retained gastric contents, perioperative regurgitation, and pulmonary aspiration syndrome, and this is a concern for anesthesiologists and patients taking these medications.

The American Society of Anesthesiologists recently released a consensus-based statement that recommends patients on daily dosing hold incretin-based therapy the day of the procedure, and those on weekly dosing hold the medication a week before the procedure. The evidence for these recommendations is based on retrospective studies and case reports, and therefore the conclusions may be overly prescriptive. Furthermore, holding incretin-based therapy poses a risk for worsening diabetes control and more importantly, could cause unnecessary delays in care if a patient's procedure is postponed because they failed to hold the medication based on the recent recommendations (1-3).

Study Objective:

To assess whether holding incretin-based therapy before endoscopy reduces the likelihood of clinically relevant Residual Gastric Volume (RGV).

Hypothesis:

Holding incretin-based therapy is non-inferior to continuing incretin-based therapy for reducing the risk of clinically relevant RGV.

Study design:

Randomized Non-Inferiority Controlled Trial.

Blinding:

Single-blind: endoscopist and anesthesia team will be blinded to study group assignment.

Primary Outcomes:

The primary outcome is clinically significant residual gastric volume defined as a composite of the following variables:

- Residual gastric volume that precludes adequate endoscopic examination
- Residual gastric volume that necessitates premature termination of the endoscopy procedure
- Need for endotracheal intubation due to stomach contents.
- Occurrence of aspiration events requiring extended observation/monitoring, unplanned therapeutics, and/or hospital admission

Secondary Outcomes:

- Presence of any solid food
- Presence of moderate liquid content
- Increased RGC defined as any amount of solid content or $> 0.8 \text{ mL/Kg}$ of fluid content (measured from the aspiration/suction canister).
- Aspiration events up to 48 hours after endoscopy
- Differences in primary and secondary outcomes between different medications

Inclusion Criteria:

- Patients using incretin-based therapies at a stable dose for more than 1 month.
- Understand the study procedures and will be able to provide written informed consent to participate in the study.
- Patients scheduled for outpatient esophagogastroduodenoscopy (EGD), combined EGD and colonoscopy, endoscopic ultrasound (EUS), or endoscopic retrograde cholangiopancreatography (ERCP) under monitored anesthesia care (MAC) or moderate sedation.

Exclusion Criteria:

- Documented history of gastroparesis (based on a 4-hour solid-phase gastric emptying study)

- Known history of achalasia
- Surgical or genetically altered foregut anatomy
- Known gastric outlet obstruction or pre-procedure imaging suggestive of gastric outlet obstruction.
- Patients who did not follow the standard NPO (nil per oral) instructions.
- Patients who have planned endotracheal intubation (ETT) during their upper endoscopy procedure (EGD, EUS, or ERCP).
- Ongoing opiate use
- Unable or unwilling to give written consent

Randomization:

- Patients will be randomly assigned to either continue incretin-based therapy as prescribed (“continue” group) or to hold therapy as outlined in the ASA guidance recommendations (“hold” group).
- Simple randomization will be applied post-enrollment, utilizing REDCap serial numbers with pre-determined interventions (“continue” vs. “hold”). The randomization table of allocation will be completed by a statistician on REDCap to ensure concealed allocation.

Study Operation:

- The candidates for the study will be determined either during the gastroenterology clinic visit OR based on review of records by a member of the research team of patients scheduled for upper endoscopy, EUS, and ERCP cases three to four weeks in advance
- Patients’ invitation
 - For patients who are scheduled for the procedure through the gastroenterology clinic, the patient’s clinic provider will invite the patient for the study during the office visit or with a phone call.
 - For patients who are not scheduled via the above route, a letter of invitation will be sent to the patient from the physician completing the procedure through the US mail or MyChart.
- Patient consent
 - Interested patients in the clinic setting will be given the option to complete a research encounter during the same day, including in-person consent if interested, or complete the process remotely over the phone and through MyChart Electronic consent, or DocuSign.
 - Patients who are not identified in clinic but through chart review will receive a phone call and phone encounters will be completed with interested potential participants and will include an explanation of the study and the consent process (phone scripts attached). MyChart Electronic consent process or DocuSign will be used to send the study consent to the participants.
- After obtaining consent, the patient information will be entered into the REDCap which will give the patient a REDCap serial number.

- A randomization tool in the REDCap will determine the intervention (The randomization table of allocation will be completed by a statistician on REDCap to ensure concealed allocation).
- The patient will be informed about the intervention during the clinic visit by a study member (not the endoscopist) or over the phone.
- A few days before the intervention, the patient will receive a call as a reminder of the intervention and instruction from a study member (not the endoscopist).
- On the endoscopy day, the proceduralist and anesthesia team will be blinded to the patient's group assignment. To ensure that blinding is maintained, a sticker will be placed on the patient physical chart to remind the provider to avoid asking about the study intervention.
- A research coordinator/investigator will confirm intervention compliance and record the variables of interest for the study.
- Information will be directly entered into the Redcap data collection sheet or recorded on a physical paper-based collection sheet and transferred immediately to Redcap on the same day. The physical sheets will be shredded on the day of the procedure.
- A phone call to the patient within the first week after the procedure to follow up and exclude aspiration events. If patient cannot be contacted, then a member of the study team will review patient records to identify any emergency department visits or hospitalizations related to a post-procedure aspiration event.

Electronic Consent operation

- An investigator or research coordinator will contact the invited candidates over the phone 2-4 weeks before the scheduled procedure. The study purpose, intervention, adverse events, and consenting process will be discussed over the phone. The encounter will be documented in the patient chart as a phone encounter.
- Subjects interested in the study will be provided with consent through MyChart Electronic consent or DocuSign with instructions to complete online consent signing.
- After all parties complete the consent, a randomization of the study intervention will be done through Redcap.
- A follow-up phone call will be made to communicate the instructions to the participants.

Rational for electronic consent (E-consent)

The study is not feasible with conventional consent, especially for open access procedures for the following reasons:

- The duration for participant involvement in the study is short, and the study intervention is only applied one week before the procedure, which would make it impractical to bring the patient for an extra encounter and would decrease the chance for enrollment.

- Many procedures are scheduled in an open-access fashion, which means that the patient is scheduled for the procedure by a provider other than the performing physician and/or from a different department.
- The intervention for the study must be completed one week before presenting to the procedure, which requires that the patient be enrolled before the procedure date.

Sample Size Determination:

- Previous retrospective studies indicate that 5-7% of GLP-1RA users have increased RGV compared to less than 0.5% in non-users.
- If there is a significant difference in favor of the experimental (“hold”) group of 7%, then 120 patients are needed (60 in each group) to be 80% certain that the upper limit of a one-sided 95% confidence interval (or equivalently a 90% two-sided confidence interval) will exclude a difference in favor of the standard group of more than 3% (the non-inferiority limit) using Farrington-Manning’s score test.
- Because estimates from previous retrospective studies are for the outcome of residual gastric volume, they may not accurately reflect our primary outcome, which is a more pragmatic and clinically useful outcome. Therefore, we plan to conduct an interim analysis at 20% recruitment and may adjust sample size if necessary, based on point estimates derived from the interim analysis.

Study Variables

Date of birth, gender, race, body mass index (BMI), type of incretin-based therapy used, incretin therapy dose, pre-endoscopy clinical symptoms, presence of diabetes, last HbA1c if available, detailed endoscopic reports, gastric residual content on endoscopy, and RGC-related events as described above. Please refer to the data collection sheet for details of the variables above.

Study Statistics

The Statistics will be done with the help of a Cleveland Clinic statistician. Data will be extracted in deidentified form directly from Redcap for analysis.

Once data has been collected, we will use STATA version 14.1 (STATA Corp, College Station, TX, USA) for statistical analysis. We will use statistics of central tendency (mean, median, and mode) for most values. Data normality will be tested using Kolmogorov-Smirnov test. We will use Pearson’s chi-square tests for categorical variables and T-test for continuous variables. A P-value of < 0.05 will be considered significant for all statistical analyses. The primary outcome will be calculated using chi-square or Mann-Whitney test. For the primary outcome, an intention-to-treat analysis will be utilized.

Interim Analysis and Data Monitoring Committee (DMC)

The study DMC will include the following: The gastroenterology program director at Weston, a gastroenterologist, and a Cleveland Clinic statistician. Meetings will be held at 20%, 50, and 100% of recruitment to ensure data security compliance, appropriate rate of recruitment, and study adverse events monitoring. A report of each meeting will be sent to the IRB. The DMC will not be blinded for study groups. Interim analysis will be conducted after 20 and 50% of recruitment on the second DMC meeting, and the study will be stopped if inferiority is confirmed.

Data Security

Data, including patient information and consent, will be stored electronically in the Redcap system\DocuSign which is password-protected and on the secure Cleveland Clinic network. If physical paper sheets were used, the physical paper sheets' information would be transferred to Redcap and shredded on the day of data gathering.

Possible Harm to Subjects and Adverse Events

The study risk is related to continuing incretin-based therapy in the periprocedural time. Medication continuation has a theoretical risk of increased residual gastric content, although there is no strong evidence to support that. Increased gastric residual content can lead to prolonged monitoring time, increased procedure time, premature termination of the procedure, unexpected urgent endotracheal intubation, or aspiration events.

Breach of confidentiality is another potential harm, and it will be minimized by the data security plan described above. The study does not involve prescribing incretin-based therapy.

All serious unexpected adverse events will be recorded and reported to the IRB in a timely fashion. Adverse events (study outcome) will be reported to the IRB after each DMC meeting.

References

- 2- Silveira SQ, da Silva LM, de Campos Vieira Abib A, et al. Relationship between perioperative semaglutide use and residual gastric content: A retrospective analysis of patients undergoing elective upper endoscopy. *J Clin Anesth.* 2023;87:111091. doi:10.1016/j.jclinane.2023.111091

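### The trial is designed and sized to show hold non-inferior within 3 points, but the named primary test never tests that limit, and the Objective asks about a reduction

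*Combined protocol and SAP*

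**What the plan says.** Four places in the combined protocol and SAP bear on the primary question.

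- **Study Objective:** "To assess whether holding incretin-based therapy before endoscopy reduces the likelihood of clinically relevant Residual Gastric Volume (RGV"). This is a question about a reduction.
- **Hypothesis and Study design:** "Holding incretin-based therapy is non-inferior to continuing incretin-based therapy for reducing the risk of clinically relevant RGV". The design line also calls the trial a non-inferiority trial.
- **Sample Size Determination:** 60 per arm, 80% power, Farrington-Manning score test. The criterion, judged on a one-sided 95% (two-sided 90%) interval, is that its upper bound "will exclude a difference in favor of the standard group of more than 3% (the non-inferiority limit"). Hold is labelled experimental and continue standard. The same section warns of the retrospective rates that "they may not accurately reflect our primary outcome", and that the team "may adjust sample size if necessary, based on point estimates derived from the interim analysis".
- **Study Statistics:** "The primary outcome will be calculated using chi-square or Mann-Whitney test", with a general significance level of P<0.05 and intention-to-treat for the primary outcome. It mentions no limit, no interval for the difference and no Farrington-Manning test.

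The DMC section stops the study on confirmed inferiority without naming the arm or the contrast.

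**The concern.** A chi-square test, or a Mann-Whitney test on a binary outcome, asks whether the arms differ at all. It cannot show that holding is no more than 3 points worse. A non-significant result is compatible with a large disadvantage, and non-inferiority can be met when the test is far from significant. So the analysis section, followed as written, does not test the Hypothesis.

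The Objective is a separate mismatch. Showing that hold is not more than 3 points worse is weaker than showing that it reduces residual volume. A report could meet the Hypothesis and be read as answering the Objective when it does not. The reverse misreading is also possible. The Background says of the current guidance that "therefore the conclusions may be overly prescriptive", so some readers will look for reassurance about continuing. Non-inferiority of hold gives none.

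**Working it through.** **Inputs.** From Sample Size Determination: 60 per arm, limit 3 points, one-sided 5%, 80% power, an anticipated 7-point difference in favour of hold, residual-volume rates of 5–7% in users and below 0.5% in non-users. The rate in each arm is not stated. I assume continue 7% or 5% and hold 0.5%, and also 0% versus 7%, which gives the stated 7 points exactly.

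**Reproducing the 120.** Farrington-Manning size per arm:

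n = [(1.645·s₀ + 0.842·s₁) / (p_continue − p_hold + 0.03)]²

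Here s₁² is the sum of p(1−p) over the arms at the assumed rates, and s₀² is the same sum at the restricted maximum-likelihood rates with hold 3 points above continue. For 0.5% versus 7% the restricted rates are 6.58% and 3.58%, so s₀ = 0.3099 and s₁ = 0.2647.

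n = [(0.5098 + 0.2228) / 0.095]² = 59.5, that is 60 per arm and 120 in all.

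The stated size is therefore reproduced for non-inferiority of hold. (0% versus 7% gives 52 per arm.)

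**Same data, two criteria, 60 per arm.** The non-inferiority statistic is z = (p̂_hold − p̂_continue − 0.03)/SE, with SE from the restricted rates. The upper limit comes from inverting that test. Chi-square is Pearson, uncorrected.

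| Events, hold vs continue | Non-inferiority p | Upper limit, hold − continue | Chi-square p |
|---|---|---|---|
| 2 vs 2 | 0.197 | +6.7 points | 1.0 |
| 0 vs 1 | 0.044 | +2.7 points | 0.32 |
| 0 vs 2 | 0.023 | +1.1 points | 0.15 |
| 1 vs 4 | 0.025 | +1.3 points | 0.17 |

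Worked cases:
- 2 vs 2: z = (0 − 0.03)/0.0352 = −0.85, so non-inferiority is not shown.
- 0 vs 1: z = (−0.0167 − 0.03)/0.0274 = −1.71, so it is met. The chi-square statistic is 1.01.

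**Exact power at 60 per arm.** I enumerated all 61 × 61 outcomes and summed their binomial probabilities.

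| Hold vs continue (assumed) | Hold non-inferior | Reduction, two-sided chi-square | Reduction, one-sided 5% | Non-inferior, but two-sided chi-square shows no reduction |
|---|---|---|---|---|
| 0.5% vs 7% | 92% | 48% | 69% | 44% |
| 0.5% vs 5% | 84% | 27% | 47% | 57% |
| 0% vs 7% | 99% | 61% | 80% | 37% |

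The exact 92% exceeds the formula's 80% because events are few and the normal approximation is rough. If the composite is rarer than the residual-volume rates (assumed 3% or 2% versus 0.5%), non-inferiority power is 68% or 55%, and one-sided reduction power 21% or 9%.

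**The case against.** The strongest reply is that the plan does have a criterion. The design line, the Hypothesis and the sample-size paragraph all point to non-inferiority, with a limit, a method and a confidence level. On that view the chi-square sentence is loose drafting and the Objective is one poorly worded sentence. Much of this stands. A reader might infer that the plan has no decision rule, or that the rule is meant to be picked after the data are seen. The documents do not support either reading. What remains is that the sample-size criterion is never carried into the analysis section, which names a different test for the primary outcome.

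A reader might also infer that 120 patients and 80% can be obtained only for non-inferiority. That fails: at 0% versus 7%, one-sided 5% power for a reduction is also 80%. But one-sided testing of a reduction appears nowhere in the plan. Pearson's chi-square on a 2×2 table is non-directional, so P<0.05 is naturally two-sided, and power is then 61%.

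Finally, a reader might infer that the Hypothesis must become a superiority hypothesis, or that enrolment must rise. Neither follows. Which claim is primary is the sponsor's choice, and if non-inferiority is kept the 120 stands on the plan's own inputs.

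On the interim rule, labelling hold as experimental makes hold the natural subject of inferiority. Yet Possible Harm to Subjects places the study risk in continuing, so the wording needs reconciling. This is a clarification and not the main fault.

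**Conclusion.** The concern holds. The Hypothesis, design and sizing concern non-inferiority of hold within 3 points; the named primary test does not test that limit; and the Objective asks about a reduction, which meeting the limit does not establish. The conflict between limit and test rests on the text and on the event-count examples, which need no assumed rates.

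The power figures do rest on assumed arm rates taken from residual-volume data, which the plan itself says may not carry over to the composite. On those rates the stated 80% belongs to the non-inferiority criterion and not to the P<0.05 test, for which power to show a reduction is 27% to 61%. The one coincidence is the one-sided 5% reduction test at 0% versus 7%. The sample-size arithmetic is not in error.

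**What to change.** 1. **Study Statistics:** for the primary outcome, replace the chi-square or Mann-Whitney sentence with the two-sided 90% Farrington-Manning interval for hold minus continue. Conclude non-inferiority of hold only if its upper limit is below +3 points.
2. **Objective, Hypothesis and design line:** make them agree. If non-inferiority is kept, reword the Objective and state that meeting the limit is neither evidence of a reduction nor reassurance about continuing. Claim a reduction only from a separately stated superiority test, done after non-inferiority is met, with its level and sidedness given. If a reduction is to be the primary claim, change the Hypothesis and the design line as well.
3. **Sample Size Determination:** state the arm rates behind the 80%, say that it applies to non-inferiority of hold, and add the power of 120 patients for a reduction over a range of rates.
4. **Interim Analysis and DMC:** say which arm and contrast inferiority refers to, and reconcile this with the Hypothesis and with Possible Harm to Subjects.

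The cost is text only. The downside is a visibly less favourable power for the reduction question. No increase in enrolment is required by these changes.

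### Wrong as written: the non-inferiority test can only show that holding is not worse than continuing, which matches neither the stated objective nor the rationale for the trial

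*Combined protocol and SAP*

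**What the plan says.** Four parts of the combined protocol and SAP bear on what the trial is meant to show.

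- **Study Objective:** "To assess whether holding incretin-based therapy before endoscopy reduces the likelihood of clinically relevant Residual Gastric Volume (RGV". This is a superiority question.
- **Hypothesis:** "Holding incretin-based therapy is non-inferior to continuing incretin-based therapy for reducing the risk of clinically relevant RGV". This is a non-inferiority claim for holding.
- **Sample Size Determination:** "If there is a significant difference in favor of the experimental (“hold”) group of 7%, then 120 patients are needed (60 in each group", where the limit "will exclude a difference in favor of the standard group of more than 3% (the non-inferiority limit) using Farrington-Manning’s score test". Hold is the experimental arm, continue is the standard arm, and the margin rules out only that hold is worse.
- **Background and Possible Harm to Subjects and Adverse Events:** of the guidance to hold, the Background says "therefore the conclusions may be overly prescriptive", and it names costs of holding (diabetes control, postponed procedures). The harm section says "The study risk is related to continuing incretin-based therapy in the periprocedural time", then calls that risk theoretical and not backed by strong evidence.

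Study Statistics names a chi-square or Mann-Whitney test for the primary outcome. It gives no margin, no interval, and no decision rule for either direction. The Farrington-Manning method appears only in the sample-size text.

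**The concern.** Non-inferiority suits an option that has other advantages but might be somewhat worse on the primary outcome. Here the Background lists disadvantages of holding, the harm section places the study risk in continuing, and the sample-size text expects hold to do better. Showing that hold is not more than 3 points worse is therefore a weak statement. It does not establish that holding reduces risk, which is the objective. It also says nothing favourable about continuing, which is where the rationale points.

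At stake is what a positive result would mean. The criterion is most easily met when continuing is clearly worse, and it usually fails when the arms are alike. As no other reading of the data is specified in advance, a claim about continuing would have to rest on a limit chosen after the results were known.

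**Working it through.** **Inputs.** Margin 3 points, one-sided 5%, 80% power and 60 per arm come from Sample Size Determination. The event rates start from the same section: "Previous retrospective studies indicate that 5-7% of GLP-1RA users have increased RGV compared to less than 0.5% in non-users". I take 7% for continue and 0.5% for hold. The second is an assumption, since the text says less than 0.5% and refers to non-users.

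**1. The plan's own figure.** With hold as the protected arm, the Farrington-Manning formula is

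n = [(z₀.₉₅·s₀ + z₀.₈₀·s₁) / (0.03 − (p_hold − p_cont))]²

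- s₁ = √(0.005×0.995 + 0.07×0.93) = √0.070075 = 0.2647.
- Rates restricted to the null: 0.0658 (hold) and 0.0358 (continue), so s₀ = √(0.0658×0.9342 + 0.0358×0.9642) = 0.310.
- Denominator: 0.03 + 0.065 = 0.095.
- n = [(1.645×0.310 + 0.842×0.2647)/0.095]² ≈ 59.5, so 60 per group and 120 in total.

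The stated size reproduces in this direction (asymptotic power 80.4% at 60 per arm). It corresponds to a 6.5-point difference. A literal 7 points gives 52 per group (0% v 7%) or 57 (0.5% v 7.5%).

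**2. Exact chance of each claim at 60 per arm.** The same score test was applied to every pair of event counts, in both directions, and weighted by binomial probabilities. The equal-rate rows are assumed scenarios.

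| True rate, hold | True rate, continue | Hold shown within 3 points | Continue shown within 3 points |
|---|---|---|---|
| 0.5% | 7% | 92.3% | 0.35% |
| 0.5% | 5% | 84.2% | 1.2% |
| 0.1% | 0.1% | 5.5% | 5.5% |
| 0.2% | 0.2% | 10% | 10% |
| 0.5% | 0.5% | 19.3% | 19.3% |
| 1% | 1% | 25.5% | 25.5% |
| 2% | 2% | 25.4% | 25.4% |
| 3% | 3% | 22.5% | 22.5% |
| 5% | 5% | 17.8% | 17.8% |
| 7% | 7% | 14.9% | 14.9% |

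No pair of counts at 60 v 60 satisfies both claims. Even 0/60 in both arms gives z = −1.36 in each direction, short of −1.645, with an upper limit of 4.3 points.

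**3. Examples of success as written.**

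- Hold 0/60, continue 1/60: z = −1.706, so the criterion is met. The upper one-sided 95% limit for continue minus hold is 7.1 points, so continuing is not shown to be within 3. Tested against 0, the difference is 1/60 = 0.01667 with pooled standard error √(2×(1/120)×(119/120)/60) = 0.0166, a ratio of 1.00 against 1.645. So holding is not shown to reduce risk either.
- Hold 0/60, continue 4/60: the criterion is met (z = −2.49), and the upper limit is 14.0 points.

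**4. Distance from the objective.** At 0.5% v 7%, 44% of trials would meet the written criterion and still have a non-significant Pearson chi-square test at 5%. A design built for the objective needs about 133 per group at those rates (two-sided 5%, 80% power).

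**5. Size needed for a claim about continuing.** With the direction reversed and 80% power, Farrington-Manning gives 168 per group at equal rates of 0.5%, 224 at 1%, 334 at 2%, 683 at 5% and 915 at 7%. At 0.5% v 7% no size suffices, because the true difference of 7 − 0.5 = 6.5 points exceeds the margin.

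**The case against.** The strongest reply is that the hypothesis, arm labels, assumed effect and margin agree with one another. Hold departs from therapy as prescribed, so calling it experimental is defensible. No section makes the acceptability of continuing an objective, and doubt about the guidance is equally compatible with asking whether holding does any good. All of this stands.

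A reader might therefore go further than the documents allow in three ways. The first is to say that the test protects the wrong arm and the roles must be swapped. That chooses the sponsor's question for it, and the only stated objective concerns a benefit of holding. The second is to say that a positive result would be reported as permission to continue. Nothing in the documents draws that conclusion. The third is to treat continuing as an established hazard, whereas the protocol calls its risk theoretical.

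The rates are also uncertain. Sample Size Determination itself warns that they concern residual volume and may not carry over to the composite outcome. This limits the precision of the percentages.

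The mismatch survives these points. Even if hold is properly the experimental arm, non-inferiority of hold does not answer the stated objective and gives no support to continuing.

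**Conclusion.** The concern holds as an inconsistency between rationale, objective and hypothesis direction. It is not an arithmetic error, since 120 patients follow from the plan's inputs once 0.5% v 7% is assumed. At those rates the written criterion succeeds in 92% of trials by exact calculation, and continuing would be shown within 3 points in 0.4%. At assumed equal rates of 0.5% to 7% either claim succeeds in about 15% to 26%. That range is not a lower bound for a rare composite: power falls to about 5% to 10% at 0.1% to 0.2%. The finding that no counts at 60 v 60 meet both claims does not depend on any assumed event rate. It does depend on equal arms of 60, which simple randomization does not guarantee. The documents do not settle which question the sponsor intends, so the sections must be reconciled.

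**What to change.** 1. Reconcile Study Objective, Hypothesis, the margin direction in Sample Size Determination, and the primary test in Study Statistics, so that all four state the same question. The stopping rule for inferiority should name the arm it refers to.
2. In Study Statistics, make the two-sided 90% Farrington-Manning interval for continue minus hold the primary analysis.
3. State in advance how it will be read:
   - a lower limit above −3 points shows only that hold is not worse by the margin;
   - a lower limit above 0 shows that holding reduces risk (at one-sided 5%, which should be squared with the general P < 0.05 rule);
   - only an upper limit below +3 points supports continuing.
4. Beside the 80%, give the power for the claim about continuing at 60 per arm, with the assumed rates: 0.4% at 0.5% v 7%, about 15% to 26% at equal rates of 0.5% to 7%, and about 5% to 10% at 0.1% to 0.2%.
5. Do not present a reversed primary hypothesis at 60 per arm as adequately powered.

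The cost is wording and one added interval, which the current analysis section does not plan. The downside is a much less favourable stated power for the claim about continuing. These changes need no added patients or procedures. A trial powered to support continuing would need far more patients, as the working shows.

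### Minor, cheap improvement: simple randomisation does not hold the 60-per-group split that the sample size assumes; concealed, randomly varying permuted blocks stratified by dosing interval would

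*Combined protocol and SAP*

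**What the plan says.** The Randomization section of the combined protocol and SAP sets the method: "Simple randomization will be applied post-enrollment, utilizing REDCap serial numbers with pre-determined interventions". It adds: "The randomization table of allocation will be completed by a statistician on REDCap to ensure concealed allocation". No blocking and no stratification factor appear anywhere.

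The Sample Size Determination section gives "120 patients are needed (60 in each group", for 80% power with a one-sided 95% interval, a 3-point non-inferiority limit and the Farrington-Manning score test. It makes no allowance for unequal arms. It cites earlier retrospective work in which "5-7% of GLP-1RA users have increased RGV compared to less than 0.5% in non-users".

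The hold group follows the anesthesiology society's guidance, which the Background summarises as "patients on daily dosing hold incretin-based therapy the day of the procedure, and those on weekly dosing hold the medication a week before" the procedure. What a patient in the hold group does therefore depends on dosing interval. Secondary Outcomes include differences between medications. The documents do not give the mix of daily and weekly users.

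**The concern.** The calculation uses equal arms, and the allocation method leaves arm sizes to chance. Few events are expected: at 7% vs 0.5% with 60 per arm, 60 × 0.07 + 60 × 0.005 = 4.5 in total. With so few, the score test's pass/fail boundary moves in whole events and can shift when a few patients fall in one arm rather than the other.

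Dosing interval determines what holding means, yet nothing keeps daily and weekly users balanced between the arms. That affects how comparable the groups look at baseline and how well the between-medication comparison is supported.

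**Working it through.** **Inputs.** From Sample Size Determination: N = 120 at 1:1, margin 0.03, one-sided alpha 0.05 (z = 1.645), Farrington-Manning test. The section states a 7-point difference but not the two rates. Assumed here: continue 7% and hold 0.5%, the ends of the cited ranges. That is a 6.5-point difference, but it is the pair that returns exactly 60. Other pairs give 52 (7% vs 0%), 57 (7.5% vs 0.5%) and 62 (8% vs 1%) per arm.

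**1. Reproduce the plan's figure.** Power = Φ[(margin − Δ − 1.645·s0) / s1], where Δ = hold − continue = −0.065, s0 is the standard error under the restricted null estimates (0.0658 hold, 0.0358 continue) and s1 is the standard error under the assumed rates. At 60/60, s0 = 0.0400 and s1 = 0.0342:

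(0.03 + 0.065 − 1.645 × 0.0400) / 0.0342 ≈ 0.85, so power = 80.35%. The stated 60 per arm is reproduced.

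**2. Arm sizes under simple randomisation.** Hold-arm size ~ Binomial(120, 0.5), SD = √(120 × 0.25) = 5.5.
- P(exactly 60/60) = 7.3%
- P(gap of 20 or more) = 8.2%
- P(hold arm of 56 or fewer) = 26%
- Central 95% range: 49/71 to 71/49

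**3. Asymptotic power averaged over the splits.** 80.02% against 80.35%, a loss of 0.33 points. N = 121 recovers it (80.34%). The effect depends on direction (hold/continue): 54/66 gives 78.5%, 49/71 gives 76.1%, 66/54 gives 81.4% and 71/49 gives 81.9%. Power rises in 46% of allocations.

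**4. Exact power.** Every outcome table is enumerated with the same test, then averaged over the binomial split. Hold rate 0.5% throughout.

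| Continue rate | 60/60 | Average, simple randomisation | Loss (points, before rounding) | Source of rate |
|---|---|---|---|---|
| 7% | 92.3% | 90.1% | 2.3 | cited range |
| 5% | 84.2% | 80.1% | 4.1 | cited range |
| 3.5% | 73.3% | 67.3% | 6.0 | assumption only |
| 2% | 54.7% | 47.0% | 7.7 | assumption only |

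**5. Why the exact loss is larger.** With 0 hold events and 1 continue event, the score z is −1.71 at 60/60, which passes the −1.645 cut-off. At 56/64 it is −1.63, which does not. Losing that one result takes exact power at 56/64 to 86.3% (7% vs 0.5%) and 71.9% (5% vs 0.5%). The path is not smooth: at 7% vs 0.5%, 59/61 gives 92.8%, 54/66 gives 87.6% and 70/50 gives 92.3%.

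**6. Dosing mix.** Assume 20 to 50% daily users, a continue-arm rate of 0 to 2% among them, and 7% overall. Simulated power of the unadjusted test at 60/60 is 92.4 to 92.7% when stratified by dosing and 92.3 to 92.6% when not, a difference of about 0.1 point or less. The SD of the between-arm difference in daily share is √[s(1 − s) × 2/60], which is 7 to 9 percentage points for s = 0.2 to 0.5.

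**The case against.** The strongest reply is that simple randomisation is legitimate, clearly stated and the least predictable method. Under Study Operation, a study member tells each patient the assignment, and that person is not said to be blinded. Staff can therefore know past allocations and could partly guess the end of a block. This stands: the present method has a real advantage, and any blocking must protect it.

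It also stands that the formula behind the 60 per arm shows almost no loss, that both exact averages at the cited rates stay above 80%, and that part of the exact gap is a favourable step near 60/60. The worst-case exact size of the test there is 5.2%, so that benchmark is slightly generous.

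The one-event threshold applies only if Farrington-Manning is the final test. Study Statistics names chi-square or Mann-Whitney for the primary outcome, a separate matter to reconcile.

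Finally, blocking does not guarantee 60/60. Blocks can end incomplete, and failure to follow fasting instructions, an exclusion, becomes known only after randomisation. The fix keeps the arms near the planned split; it does not fix them there.

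**Conclusion.** The point holds as a minor one. The allocation method does not deliver the equal split used for sizing, and nothing balances dosing interval. The average cost is about 0.3 points of power by the plan's own formula. By exact enumeration it is about 2 points (7% vs 0.5%) to 4 points (5% vs 0.5%), assuming those rate pairs and Farrington-Manning as the decision rule.

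A reader might infer more, and the documents do not support it:
- **A loss of 6 to 8 points.** This needs continue-arm rates of 3.5% or 2%, which the documents do not give. The protocol does concede that the cited rates may not reflect its composite outcome. At 2%, however, power is only 54.7% even at 60/60, so the event rate would be the problem.
- **Any uneven split lowers power.** It does not; the direction matters and the exact curve is not monotone.
- **Chance imbalance in dosing costs power or biases the result.** The power cost is about 0.1 point or less over the mixes assumed, and chance imbalance is already covered by the test's error rate. The case for stratifying is comparability and the between-medication outcome.
- **Simple randomisation brings no benefit.** It gives the least predictable next assignment.

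**What to change.** In the Randomization section, replace simple randomisation with 1:1 permuted blocks of randomly varying size, stratified by dosing interval (daily vs weekly). Generate them in the same statistician-prepared REDCap table. Keep the block sizes out of the protocol and unknown to staff who enrol patients or tell them their assignment.

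The cost is one wording change and a differently generated list, with no added patients, visits or staff. The downside is slightly more predictable allocation; varying block sizes and the existing REDCap concealment limit it.
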